12.0 Statistical Considerations

We performed sample size/power calculations with the primary outcome of pain (visual analog scale) at the time of Carevix[™]/tenaculum use. Thirty participants per group (total N=60) are needed to achieve at least 80% power and a two-sided 5% significance level. Descriptive characteristics of those in the Carevix[™] and control groups will be compared using standard statistical testing such as Chi-square and t-tests. Differences in outcomes between the device and control groups will similarly utilize standard testing.

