5.0 Study Design

Aspivix, the company that created Carevix[™], launched the Ambassador Program, a 3-6 month program with free of charge devices for clinics willing to test Carevix[™] in multiple intrauterine procedures. Our clinic, Coleman Center, will conduct a prospective cohort study for 3-6 months where patients who qualify via inclusion criteria who are also receiving an intrauterine procedure (endometrial biopsy, IUD insertion, manual aspiration, etc) on the exposure (Carevix[™]) arm will have the opportunity to receive the Carevix[™] device for cervical stabilization, per provider preference (i.e., providers may decline to use Carevix[™] for endometrial biopsy).

Once 25 participants have received Carevix[™], recruitment for the control (tenaculum) arm will begin. Participants will receive the standard of care device if cervical stabilization is required. Each participant will be provided with a study information sheet and sign a consent form. They will then undergo their planned procedure, using the assigned device.

Following completion of their procedure, they will also agree to fill out a survey about their experience, which takes about 1 minute to complete. The provider performing the procedure will finish the survey with provider-specific questions about bleeding, ease of use and satisfaction. The purpose of this study is to compare Carevix[™] to the tenaculum and determine if the Carevix[™] shows similar results in the United States population as it has in the European study and with all intrauterine procedures.

*Once 25 of 30 patients received CarevixTM, will commence control group collection N = 30

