6.0 Enrollment

We intend to enroll twenty-five evaluable Carevix subjects prior to commencing the enrollment of the control-group tenaculum subjects. An additional five Carevix subjects (for a total of N=30) will be concurrently enrolled while accruing the thirty additional tenaculum subjects for a total enrollment of N=60.

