7.0 Study Procedures

Any intrauterine procedure already scheduled will otherwise proceed accordingly as part of clinical care. During the enrollment, patients who fit above inclusion criteria and are scheduled for an intrauterine procedure may be offered the opportunity to participate in this program and trial the new Carevix[™] device during the exposure recruitment period and complete a short survey. If the patient consents to the use of Carevix[™] Ambassador program, the suction-based cervical stabilizer will be used on their cervix to stabilize the cervix during the procedure instead of the traditional tenaculum. If the patient or provider opts out of the use of Carevix[™], they will be asked if they'd like to participate in the study with the tenaculum. During the tenaculum enrollment phase, patients will receive the standard of care device and complete a short survey.

Following completion of the procedure, the patient will then fill out the patient-based survey. Following the completion of the patient's questions, the provider will then fill out the provider-based survey.

The questionnaire for the Carevix[™] Ambassador program will be stored within the Aspivix company database (all questions are HIPAA compliant and do not reveal PHI). The survey is labeled as originating from Indiana University for easy access to only our patient data.

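### Device is tied to enrolment phase and, through opt-outs, possibly to procedure type, yet Section 12 compares outcomes with unadjusted standard tests

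*Combined protocol and SAP*

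**What the plan says.** Section 12.0 sizes the study on the "primary outcome of pain (visual analog scale) at the time of Carevix[™]/tenaculum use". Group characteristics are to be "compared using standard statistical testing such as Chi-square and t-tests". For outcomes it adds: "Differences in outcomes between the device and control groups will similarly utilize standard testing". No section mentions covariates, stratification, matching, weighting or regression.

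The device a patient receives depends on two things.

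- **Phase.** Section 5.0: "Once 25 participants have received Carevix[™], recruitment for the control (tenaculum) arm will begin". Section 6.0 agrees: "We intend to enroll twenty-five evaluable Carevix subjects prior to commencing the enrollment of the control-group tenaculum subjects". The last five Carevix patients are enrolled alongside the 30 controls.
- **Preference.** Section 5.0 offers Carevix "per provider preference (i.e., providers may decline to use Carevix[™] for endometrial biopsy"). Section 7.0 then asks patients who opt out, or whose provider does, whether they will take part with the tenaculum.

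The procedures are mixed ("endometrial biopsy, IUD insertion, manual aspiration, etc"), and the hypothesis in Section 2.1 covers all of them.

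**The concern.** If providers decline Carevix for biopsies, the Carevix group loses biopsies. If those patients join the tenaculum group, that group gains them. Should pain differ between procedures, the raw difference between groups mixes a device effect with a procedure effect.

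The direction cannot be known from the documents. If biopsy is the more painful procedure, declining Carevix for it flatters Carevix; if it is the less painful one, it works against Carevix. A t-test cannot tell these apart. Comparing baseline characteristics is no safeguard: no action is planned if an imbalance appears, and a non-significant comparison at 30 per group does not show balance.

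**Working it through.** **The plan's own figure.** Section 12.0 gives 30 per group, at least 80% power and two-sided 5%, but no difference or SD, so the calculation cannot be reproduced forwards. Solved backwards, 30 per group has 80% power at a standardised difference of 0.72 (normal approximation) or 0.736 (t-test). At an assumed SD of 25 mm the latter is 0.736 × 25 = 18.4 mm.

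**Bias from procedure mix.** Bias = (share of the more painful procedure in tenaculum − share in Carevix) × pain gap between procedures. The rejection rates below come from simulation: 30 per group, SD 25 mm, no device effect, two procedure types, 40,000 runs per cell. Shares, gaps and SD are assumptions. With 50% against 20%:

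| Gap (mm) | Bias (mm) | t-test rejects | Device + procedure model rejects |
|---|---|---|---|
| 5 | 0.30 × 5 = 1.5 | 5.5% | 5.0% |
| 10 | 3 | 7.2% | 4.8% |
| 20 | 6 | 13.8% | 5.2% |
| 30 | 9 | 22.6% | 5.0% |

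At a 20 mm gap the t-test rejects 18% with SD 20 and 11% with SD 30.

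**How much declining produces such a mix.** If biopsy is a share q of procedures and a fraction d of biopsies is declined, the Carevix share is q(1−d) / [q(1−d) + 1 − q]. A 20% share from q = 0.50 needs d = 0.75: 0.125 / 0.625 = 0.20. That is strong channelling. With q = 0.30 and controls at 30%:

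| Biopsies declined | Carevix share | t-test rejects, 5 mm | t-test rejects, 20 mm |
|---|---|---|---|
| 25% | 0.243 | 5.1% | 5.3% |
| 50% | 0.176 | 5.1% | 6.5% |
| 75% | 0.097 | 5.2% | 8.9% |
| 100% | 0 | 5.7% | 14.4% |

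Now keep d = 0.50 and let opt-outs count as controls. With five biopsy opt-outs among 30 controls, the tenaculum share is (5 + 0.30 × 25) / 30 = 0.417, and the t-test rejects 5.3% at 5 mm and 10.7% at 20 mm. With ten, the share is (10 + 0.30 × 20) / 30 = 0.533, and it rejects 5.8% and 17.7%.

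**Masking.** Reverse the mix (20% tenaculum, 50% Carevix) and give Carevix a true benefit of 18.4 mm. At gaps of 5, 10, 20 and 30 mm the t-test detects it in 73%, 63%, 43% and 24% of studies; the adjusted model detects it in about 75%.

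**Phase.** With Carevix 25 early and 5 late, and tenaculum 0 early and 30 late, the squared correlation of device with phase is 0.714, so adjusting for phase inflates the variance by 1 / (1 − 0.714) = 3.5. Power at the 80% difference falls to about 32%. An assumed drift of 0.2 to 0.5 SD between phases gives a bias of 25/30 of that, 0.17 to 0.42 SD, and rejection in about 10% to 35% of null studies. Adjusting for procedure type does not remove this.

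**The case against.** - **The word unadjusted is not in the plan, and the list of tests is open-ended.** True. But the outcome sentence refers back to Chi-square and t-tests, and no other method appears anywhere.
- **Section 4.1 requires a provider willing to use Carevix.** Read as applying to both groups, this largely closes the channelling route, and rejection stays near 5% when the mix is equal. But Section 7.0 expressly invites provider opt-outs to join with the tenaculum. The sections conflict, and patient opt-outs and phase remain on either reading.
- **Pain at the time of device use may hardly depend on the procedure.** If it means stabiliser placement, the small gaps are the more plausible ones and the effect is slight. The wording does not settle this: under Section 7.0 the device is used during the procedure, and under Section 3.1 the questionnaire comes after it.
- **The sizes are assumed, and modest when built from declining rates.** This stands. At a 5 mm gap almost nothing happens; double-digit error needs a large gap together with heavy declining or opt-outs counted as controls.
- **Adjustment restores 5% only if procedure type is the sole confounder, and it costs power.** Both stand. Phase can be disclosed but hardly corrected, and power falls somewhat below the stated 80%.

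**Conclusion.** The concern holds and should be fixed, with medium confidence. The documents establish a non-randomised comparison, a device choice that they themselves link to procedure type, and no adjusted analysis.

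The size is not established. Under the assumptions shown, false-positive error from procedure mix runs from about 5% (equal mix or small gap) to 22.6% (50% against 20%, 30 mm gap), and a real benefit can be hidden in the same way. The phase problem is separate and may be as large; this design can hardly separate it from the device.

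**What to change.** In Section 12.0:

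1. Make the primary pain analysis a linear model with device and procedure type. Fix the categories in advance from Section 5.0: IUD insertion, endometrial biopsy, manual aspiration, other. Aspiration needs its own category: in one assumed mix, folding it into other left a 3.1 mm bias and 7.7% rejection, against 0.0 mm and 5.0% with four categories.
2. Keep the unadjusted test as secondary, and report pain and bleeding by procedure type.
3. Restrict to procedure types seen in both groups only as a sensitivity analysis.
4. State that calendar period can hardly be separated from device, since only about five Carevix patients overlap the planned control period, and that conclusions are associational.

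Reconcile Sections 4.1, 5.0, 6.0, 7.0 and 11.0 on who may enter the tenaculum group and when. Section 11.0 belongs here because it may keep some device-ineligible patients as tenaculum patients.

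**Cost.** Wording, plus one field for procedure type in both groups if the questionnaire lacks it (it was not available for review). At 50% against 20%, the unadjusted standard errors are 6.46, 6.53, 6.83 and 7.32 mm at gaps of 5, 10, 20 and 30 mm, against 6.85 mm adjusted: a loss of 6% or 5%, no change, or a gain of 6%. At 50% against 10% the loss is 12%, 11%, 7% or 1%. With four categories the loss at 5 mm is about 7% in the mix tried. Power at 18.4 mm is then about 74–75%; keeping 80% at 50% against 20% needs about 30 × 1.11, or 34 per group. A procedure type seen in only one group gives no device comparison.

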3.0 Outcome Measures/Endpoints

3.1 Primary Outcome Measures

3.1.1 Primary outcome measures: To assess patient-reported pain, a questionnaire provided by Aspivix [™] (Attachment #2) will be done after completing the procedure. This takes, on average, 1 minute to complete.

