8.0 Study Calendar

There is no study calendar – the patient will have their intrauterine procedure scheduled and will decide if they wish to participate in the Carevix[™] Ambassador program or not. The event will be a one-time procedure only when the Carevix[™] suction-based cervical stabilizer is used or the tenaculum is used.

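### No pain score is planned before the procedure, so the non-randomised pain comparison cannot allow for pain on arrival or gain precision from it; one added question and a simple model would do both

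*Combined protocol and SAP*

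**What the plan says.** **Timing of the pain measurement.** Section 3.1 says that the patient questionnaire "will be done after completing the procedure". Section 7.0 repeats this: "Following completion of the procedure, the patient will then fill out the patient-based survey". Section 5.0 agrees. Section 8.0 opens with "There is no study calendar" and describes a single event. No section describes a pain measurement before the procedure.

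**Analysis.** Section 12.0 names chi-square and t-tests for descriptive characteristics, then adds "Differences in outcomes between the device and control groups will similarly utilize standard testing". It mentions no covariate, regression, matching or weighting.

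**Allocation.** Section 5.0 describes a prospective cohort, not a randomised comparison. Section 6.0 sets the order: "We intend to enroll twenty-five evaluable Carevix subjects prior to commencing the enrollment of the control-group tenaculum subjects". Under 5.0, use of Carevix follows provider preference, and endometrial biopsy is the given example of a procedure where it may be declined. Under 7.0, a patient or provider who opts out of Carevix may be offered the tenaculum arm.

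**Sample size.** The calculation in 12.0 concerns VAS pain at device use. It states "Thirty participants per group (total N=60) are needed" for "at least 80% power and a two-sided 5% significance level", with no mean difference and no SD.

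**The concern.** A baseline score on the outcome scale is a natural covariate for a self-reported pain score, and here it could serve two purposes.

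- **Bias.** Arms formed by enrolment period, provider preference and opt-out need not be alike on arrival. Any intrauterine procedure qualifies (4.1), and none of the exclusions in 4.2 concerns pain already present. If one arm arrives with more pain and that pain carries into the procedure score, an unadjusted test attributes the difference to the device. Comparing descriptive characteristics between arms, as 12.0 plans, could reveal an imbalance in what was recorded but would not correct it, and arrival pain is not recorded.
- **Precision.** With 60 patients, the part of the between-patient variation that arrival pain explains stays in the error term.

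The measurement has to be prospective. After the procedure only a recalled value can be had, and the procedure itself may colour it.

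**Working it through.** **Inputs from the plan.** n = 30 per arm, two-sided alpha 0.05, power 80% (12.0).

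**Assumed inputs.** The documents give neither of these, so ranges are shown:
- the correlation r between baseline and procedure pain, 0 to 0.5; with both scores in SD units this is also the slope;
- the difference between arms in mean baseline pain, b, 0 to 0.4 SD.

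**Step 1: the plan's own figure.** Without a difference and an SD, the 30 per arm cannot be reproduced. Solving backwards, the normal formula gives (1.960 + 0.842) × √(2/30) = 0.723 SD. The two-sample t-test gives 0.736 SD, which is used below.

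**Step 2: precision with balanced baselines.** Adjustment multiplies the residual variance by 1 − r². The detectable difference is 0.736 × √(1 − r²), and the effective n per arm is 30/(1 − r²). Power is at a true difference of 0.736 SD (noncentral t, 57 df).

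| r | Variance removed | Detectable difference (SD) | Effective n per arm | Power |
|---|---|---|---|---|
| 0 | 0% | 0.74 | 30 | 80% |
| 0.3 | 9% | 0.70 | 33 | 84% |
| 0.5 | 25% | 0.64 | 40 | 90% |

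**Step 3: precision when baselines differ.** The full gain in step 2 and a baseline imbalance cannot both be claimed. An imbalance b inflates the variance of the adjusted difference by the factor 1 + (b²/58)/(2/30). At b = 0.4 this is 1 + (0.16/58)/(2/30) = 1.041.

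| r | Effective n per arm, b = 0.4 | Detectable difference (SD) |
|---|---|---|
| 0 | 30/1.041 = 28.8 | 0.75 |
| 0.3 | 32.97/1.041 = 31.7 | 0.72 |
| 0.5 | 40/1.041 = 38.4 | 0.65 |

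The net variance saving at r = 0.3 is then 1 − 0.91 × 1.041 = 5%, not 9%. At r = 0 there is a loss of about 4%.

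**Step 4: bias of the unadjusted difference.** Bias = slope × b. The false-positive rate is that of a two-sided t-test (58 df) with noncentrality bias × √15.

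| Slope | b (SD) | Bias (SD) | Share of 0.736 SD | False-positive rate |
|---|---|---|---|---|
| any | 0 | 0 | 0% | 5% |
| 0.3 | 0.4 | 0.12 | 16% | 7% |
| 0.5 | 0.4 | 0.20 | 27% | 12% |

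**The case against.** The best case for leaving the plan alone has five parts.

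- **Confounding is conjectured.** The selection routes described are enrolment period, provider preference by procedure, and opt-out. None mentions arrival pain, and nothing says that patients attending for scheduled procedures are in pain. This stands. A reader might infer that the device comparison is biased by arrival pain; the documents support only that it could be, unseen.
- **The sizes are assumed.** This stands. If most patients arrive with little or no pain, both the correlation and the benefit approach zero.
- **Baseline pain alone misses the documented imbalances.** This stands, and it is why procedure type belongs in the model. Provider and calendar period would remain uncontrolled.
- **The wording is looser than an unadjusted t-test.** Section 12.0 names tests only for descriptive characteristics, and Attachment #2 is not available here. A reader might infer that no baseline pain item of any kind exists. The documents support less: no prospective score is described. A recalled item in the questionnaire cannot be excluded, but 12.0 plans no use of one.
- **Linkage.** Carevix surveys sit on the company's server and are matched to consent by date and time (13.0), whereas control data are entered in RedCap. A baseline-adjusted model would depend on that match in one arm only. This stands as a cost. The linkage is already planned, so it does not rule out the change.

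**Conclusion.** The point holds as a cheap improvement. The plan describes no prospective pre-procedure pain score, and its outcome analysis is most naturally read as unadjusted, in a cohort where the arms are not formed by chance.

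Under the stated assumptions, adjustment is worth between nothing and about ten patients per arm when baselines are balanced (effective n 30 / 33 / 40 at r = 0 / 0.3 / 0.5). It is worth slightly less with a 0.4 SD imbalance (about 32 / 38 at r = 0.3 / 0.5). The unadjusted difference could carry 0 to 0.2 SD of bias, against a detectable difference of 0.74 SD. Because allocation is not randomised, possible bias is the stronger reason to act; the precision gain is modest unless the correlation is substantial. The documents do not support calling arrival pain an established confounder, or claiming that a baseline score would make the arms comparable.

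**What to change.** **Section 7.0.** Add one item on current pelvic pain, on the same VAS as the outcome. Record it in RedCap in both arms, after consent and before the procedure starts.

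**Section 12.0.** Make the primary analysis a linear model of VAS pain at device use on device, baseline pain and procedure type, with procedure types grouped if sparse. Report the adjusted difference with its 95% CI. Keep the unadjusted test as a supporting analysis. State that confounding by provider and calendar period may remain.

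**Cost.** One extra question per patient, a form change in both arms, and a few degrees of freedom. The primary model would also rely on the date-and-time linkage in 13.0. Unmatched Carevix surveys would then be missing from the primary model in one arm only, so their number should be reported. No extra staff or procedure is needed.

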3.2 Secondary Outcome Measures

3.2.1 Secondary outcome measures: To assess provider-reported bleeding, ease of use and provider satisfaction with the device, the provider will complete a questionnaire following the patient's completion of their portion of the questionnaire (Attachment #2). This takes, on average, 2 minutes to complete.

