4.0 Eligibility Criteria

4.1 Inclusion Criteria (to be assessed prior to procedure)

- Age 18 years or older
- Speaks and reads in English
- Able to consent on their own
- Will undergo any intrauterine procedure using the Carevix[™] (for exposure group) or using Tenaculum (for Control Group)
- Up to 20 providers performing this procedure
- Provider is willing to use Carevix[™] for scheduled procedure

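### Section 12.0 makes no allowance for providers who treat and rate several patients each, so p-values from standard tests may be materially off

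*Combined protocol and SAP*

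**What the plan says.** - **Providers.** The inclusion criteria in Section 4.1 list "Up to 20 providers performing this procedure". Section 6.0 plans 30 patients per arm, 60 in all.
- **Who rates.** For bleeding, ease of use and satisfaction, Section 3.2 says that "the provider will complete a questionnaire following" the patient's part. Section 5.0 confirms that this is the provider who did the procedure. Pain is reported by the patient (Section 3.1).
- **How the device is chosen.** The study is a non-randomised cohort. Section 5.0 makes use of the device "per provider preference (i.e., providers may decline to use" it, with endometrial biopsy as the example. Under Section 7.0, when the patient or the provider opts out, the patient may be asked to join with the tenaculum instead.
- **Sample size.** Section 12.0 states: "Thirty participants per group (total N=60) are needed to achieve at least 80% power", with "a two-sided 5% significance level".
- **Analysis.** Section 12.0 gives chi-square and t-tests as examples for descriptive characteristics, then adds: "Differences in outcomes between the device and control groups will similarly utilize standard testing".

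No section mentions a provider effect, an ICC, a design effect, a mixed model or a clustered standard error. Section 13.0 describes a site selector and matching of surveys to consents by date and time, but no provider code.

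**The concern.** Patients of one provider share that person's technique, case mix and rating habits. A two-sample t-test or chi-square test ignores this and counts 60 independent results.

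The damage depends on how providers and devices are combined. If some providers supply mostly one device, differences between providers are read as differences between devices, the standard error is too small, and false positives rise. If every provider uses both devices equally, provider differences cancel from the comparison but stay in the t-test's variance estimate. The test is then conservative and loses power.

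The opt-out rules make some imbalance plausible, since a provider who declines the device can still contribute tenaculum patients. Ease of use and satisfaction are the most exposed, because they are the provider's own opinions repeated over patients. Bleeding is also provider-rated, and Section 2.1 places it in the primary objective.

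**Working it through.** **The plan's own figure.** Section 12.0 gives no mean difference or SD, so 30 per group cannot be reproduced. It can only be solved backwards: d = (1.960 + 0.842) × √(2/30) = 2.802 × 0.2582 = 0.72 SD (0.74 SD with the t distribution). That assumes 60 independent patients.

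**Inputs**
- 30 per arm and two-sided 5%: Section 12.0.
- At most 20 providers: Section 4.1. The average load is therefore m ≥ 60/20 = 3. With 10 providers (assumed), m = 6.
- ICC ρ: not given. Assumed 0.05, 0.10 and 0.30.
- Split of devices within provider: not given. Assumed equal, 80/20 (half the providers favouring each device), or one device each.

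**Formula.** Let provider j contribute a_j patients to one arm and b_j to the other. Relative to the independent case, the variance of the difference in arm means is multiplied by

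F = 1 − ρ + ρ × Σ(a_j − b_j)² / 60.

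With even loads this becomes:
- equal use: F = 1 − ρ
- exact 80/20 split: a_j − b_j = ±0.6m, so F = 1 − ρ + 0.36mρ
- one device each: F = 1 + (m − 1)ρ

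The type I error of the nominal 5% test is approximately 2 × [1 − Φ(1.96/√F)].

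Example, 10 providers, ρ = 0.10, one device each: F = 1 + 5 × 0.10 = 1.50; 1.96/√1.50 = 1.600; type I error 11.0%; effective sample size 60/1.50 = 40. With 20 providers: F = 1.20, error 7.4%, effective sample size 50.

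**Results (type I error, %).** The formula columns assume even loads. The simulated columns (20,000 trials per case, no device effect) let patients fall to providers by chance, so loads and splits vary.

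| Providers | ρ | Equal use, formula | 80/20, formula | 80/20, simulated | One device, formula | One device, simulated |
|---|---|---|---|---|---|---|
| 20 | 0.05 | 4.4 | 5.0 | 5.4 | 6.2 | 6.8 |
| 20 | 0.10 | 3.9 | 5.1 | 6.0 | 7.4 | 8.5 |
| 20 | 0.30 | 1.9 | 5.3 | 8.8 | 12.1 | 15.6 |
| 10 | 0.05 | 4.4 | 5.7 | 6.3 | 8.0 | 8.2 |
| 10 | 0.10 | 3.9 | 6.4 | 7.5 | 11.0 | 11.8 |
| 10 | 0.30 | 1.9 | 9.1 | 12.8 | 21.5 | 24.5 |

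If equal use holds only on average, with patients falling to providers and devices by chance, the simulated error is about 5% throughout. For 10 providers, one device each and ρ = 0.30, the highest simulated value found was about 26%.

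At ρ = 0.01 the problem almost disappears: with 20 providers using one device each, F = 1.02 and the error is 5.2%.

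**The case against.** A reader might infer that the p-values and confidence intervals are wrong. The documents do not support that. They give neither an ICC nor the overlap between providers and devices, and the size and direction of the error depend on both. The plan does not mention confidence intervals at all.

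Three further points count against a strong reading.

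- Chi-square and t-tests are named as examples for descriptive characteristics and reach the outcomes only by analogy. The outcome analysis is therefore underspecified rather than a committed t-test. This stands, but nothing in the plan commits the analyst to account for provider.
- The limit of 20 providers is a ceiling. It fixes a minimum average of 3 patients; it does not show that every provider contributes several.
- One-device providers fit the design poorly. This is one clinic, Section 4.1 asks for a provider willing to use the new device, and tenaculum recruitment opens after 25 device patients, so many providers may use both. This makes the one-device columns an upper case. The opt-outs in Sections 5.0 and 7.0 still make exact balance unlikely.

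The outcome used for the power calculation is patient-reported pain, where the provider ICC may be small. The documents do not settle this. Finally, the questionnaire (Attachment #2) is not reproduced, so it may already collect provider identity.

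**Conclusion.** The point holds as a gap with conditional consequences. The documents establish repeated patients per provider on average, repeated ratings by the same person, a link between provider and device, and an analysis with no allowance for any of these. They do not establish that the resulting p-values are wrong, only that they may be materially off.

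For 10 to 20 providers and assumed ICCs of 0.05 to 0.3, the nominal 5% t-test runs at about 5% to 13% with an 80/20 split. With one device per provider it runs at about 8% to 26% for 10 providers and 6% to 16% for 20. With equal use it stays near or below 5%. Each figure rests on the assumed ICC, provider count and split. Fewer providers or less even loads would make the inflation larger. Ease of use, satisfaction and bleeding are likely to be affected most; the effect on pain may be small.

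**What to change.** **Data.** Record a coded provider ID for every patient in both arms, in the company survey data and in RedCap, if the questionnaire does not already do so. Report the number of patients per provider by arm.

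**Section 12.0.** Replace the general reference to standard testing of outcomes with:
- ease of use and satisfaction: a linear mixed model with device as fixed effect, a provider random intercept and small-sample degrees of freedom;
- VAS pain: the same model, at least as a pre-specified sensitivity analysis;
- bleeding: a GEE or cluster-robust analysis with small-sample correction. A provider-stratified test is less suitable, because at about 3 patients per provider many strata would contain one device only and contribute nothing.

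**Cost.** One coded field, some wording and slightly more analysis work. Interval estimates, if reported, may widen materially where providers favour one device: at F = 2.5 (10 providers, ICC 0.3, one device each) the standard error is √2.5 = 1.6 times the independent-data value. Where provider and device overlap completely, the model corrects the standard error but cannot separate the two. The table of patients per provider by arm would show how far that applies.
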